Prospective 4D Computed Tomography Angiography Of The Bicuspid Aortic Valve Apparatus: A Comparison Of Bicuspid Aortic Valves With And Without Aortic Insufficiency

Principal Investigator

[name]., Ph.D.
Department of Surgery
[name]
[name]
[name]
[contact]
Email: [contact]

Protocol Number

IRB Number

Grant Number

This work is supported by a pilot grant from the Translational Bio-Imaging Center (TBIC) of the Institute of Translational Medicine and Therapeutics (ITMAT) at the University of Pennsylvania

Initial version April 2020
Amended June 22, 2020
Amended

CONFIDENTIAL

This material is the property of the University of Pennsylvania.

Study Summary

Title	Prospective 4D Computed Tomography Angiography Of The Bicuspid Aortic Valve Apparatus: A Comparison Of Bicuspid Aortic Valves With And Without Aortic Insufficiency
Short Title	Prospective 4D CTA of BAV Competence
IRB Number	
Protocol Number	
Methodology	Longitudinal observational study
Study Duration	9 years
Study Center(s)	Single-center study (University of Pennsylvania)
Objectives	
Primary:
 
• To use medical imaging to determine the anatomical parameters (e.g., aortic valve and aortic root dimensions and dynamics) of bicuspid aortic valve competence. 
Secondary:
 
• To understand the natural history of BAV disease, including the development of aortic insufficiency and/or stenosis.• To determine the anatomical characteristics predictive of successful BAV repair.
Number of Subjects	60 subjects expected to enroll at Penn

CONFIDENTIAL

This material is the property of the University of Pennsylvania.

Main Inclusion and Exclusion Criteria	
Inclusion criteria:
 
• At least 18 years of age• Documented bicuspid aortic valve identified via clinical imaging (e.g., CT, MRI, or echocardiogram) with minimal calcification at the time of enrollment• Participant must sign the informed consent form 
Exclusion criteria:
 
• Pregnancy (determined by point of care urine pregnancy test)• Renal failure (estimated Glomerular Filtration Rate (eGFR) < 30), precluding them from receiving intravenous contrast• Documentation of previous intravenous contrast allergy (unless they are having a CT with steroid preparation as part of routine clinical care)• Previous aortic valve replacement
Intervention	
The study involves annual 4D CTA imaging of the bicuspid aortic valve for a period of 5 years. CTA is often standard of care for BAV patients, but patients in this study will receive a higher radiation dose with a 4D imaging protocol. There may also be patients enrolled in the study who have a 4D CTA for research purposes when a routine CTA is not required for clinical care.

Statistical Methodology	
Patients will be stratified into “competent” and “incompetent” BAV groups based on the severity of aortic insufficiency on routine echocardiography at the time of study enrollment. Geometrical and functional measurements (e.g., coaptation area, coaptation height, cusp surface area, aortic root diameters, valve orifice area, localized cusp thickness, and aortic cusp and root velocities) will be extracted from each 4D CTA scan to quantify valve morphology and dynamics at each study time point, as well as longitudinally. Measurements from the competent and incompetent BAV groups will be reported and compared.

Data and Safety Monitoring Plan	
The PI will be responsible for the data quality management and the ongoing safety of subjects.

Background and Study Rational

1 Introduction

The bicuspid aortic valve (BAV) is the most common congenital heart disease. The purpose of this study is to better understand the anatomy of physiologically “normal”, or competent, BAVs without stenosis or insufficiency (AI) in order to support evidence-based standardization of BAV repair surgery. Men and women over 18 years of age with a diagnosis of BAV and minimal aortic valve calcification at baseline will undergo annual 4D computed tomography angiography (CTA) scans, transthoracic echocardiograms, and history and physical assessments over the course of the 5-year study period. Patients who are pregnant, have renal insufficiency (creatinine > 2 mg/dL), or who have a contraindication to intravenous contrast will be excluded. Patients will be stratified into study groups according to baseline AI: approximately half of patients will have no to mild AI at baseline and the other half will have moderate to severe AI at baseline. Anatomical measurements will be obtained from the 4D CTA scans and analyzed at each phase of the cardiac cycle, as well as longitudinally. The 4D CTA imaging and analysis will not

CONFIDENTIAL

This material is the property of the University of Pennsylvania.

impact medical care of the study participants; the anatomical measurements will be used in the future as evidence-based standards for determining valve repair candidacy for BAV patients with AI.

This study will be conducted in full accordance with all applicable University of Pennsylvania Research Policies and Procedures and all applicable Federal and state laws and regulations. All episodes of noncompliance will be documented.

1.1 *Background and Relevant Literature*

The BAV is the most common congenital heart defect, reported to affect 0.5 – 2% of the population (Ward 2000). Since BAVs are typically imaged after a patient has developed symptoms of aortic insufficiency (AI) or aortic stenosis (AS), little is known about the geometric and dynamic anatomical features of the functionally “normal” or competent BAV, defined as a BAV without stenosis or insufficiency. Moreover, there are gaps in knowledge of the natural progression of BAV competence to BAV pathology, which most frequently manifests as AI and/or AS. There is limited data to predict if and when asymptomatic BAV patients will need to receive intervention to repair or replace their aortic valve.

BAV patients who present with AI typically range in age from 20 to 50 years old and, based on age at presentation, will survive several decades after intervention (Boodhwani et al. 2010). While aortic valve replacement is the conventional treatment for AI, it is not an ideal intervention in younger patients with non-stenotic BAVs. Bioprosthetic valves have limited durability in this patient population and will require at least one additional valve replacement over the patient’s lifetime (Aicher et al. 2011). Mechanical valves carry the risk of thromboembolic events and require life-long anti-coagulation, which limits quality of life in young patients (Salem et al. 2004). Therefore, BAV repair has become more widely adopted by surgeons in major cardiac centers in recent years, as early results have been satisfactory (Aicher et al. 2011, Svensson et al. 2014). However, repair strategies have not been standardized and are limited to single-center reports in relatively small patient series. Furthermore, techniques to determine repairability of a BAV have been adopted from normal trileaflet aortic valve studies (Schäfers et al. 2013) and there are no existing research studies of functionally normal BAV characteristics, such as coaptation height and cusp height. Such studies would help to standardize BAV repair procedures, as they would define the anatomical and dynamic valve characteristics that are needed to recreate BAV competence during valve repair surgery.

The goal of this research is to characterize the aortic valve and root geometry/dynamics of physiologically normal BAVs relative to BAVs with moderate to severe AI. While transesophageal echocardiography (TEE) is the most commonly used imaging modality to assess valve morphology and dynamics, it requires sedation and is not typically ordered for routine annual surveillance. In this study, 4D computed tomography angiography (CTA) imaging will be used to analyze aortic cusp motion and coaptation and to create four-dimensional BAV models to measure aortic root landmarks and valve characteristics over the cardiac cycle. The long-term goal of this research is to follow the natural history course of BAV syndrome and the development of AI or AS.

2 Study Objectives

2.1 *Primary Objective*

- To use medical imaging to determine the anatomical parameters (e.g., aortic valve and aortic root dimensions and dynamics) for BAV competence.

2.2 *Secondary Objectives (if applicable)*

- To understand the natural history of BAV disease, including the development of aortic insufficiency and/or stenosis.

CONFIDENTIAL

- To determine the anatomical characteristics predictive of successful BAV repair.

3 Investigational Plan

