3.1 General Design

This is a prospective observational study of patients with normally functioning (competent) and diseased (incompetent) BAVs. Patients will be stratified into two groups based on degree of baseline aortic insufficiency. Those patients with less than moderate (+2) AI will be in the “competent BAV” group, and those patients with greater than moderate (+2) AI will be in the “incompetent BAV” group. Each group will be limited to 30 patients. All patients will follow the same study time course and undergo the same study procedures, including an annual 4D CTA scan. The goal of this work is to describe differences in the anatomical and functional characteristics of BAVs in these two groups based on 4D CTA.

Overview of study procedures (described in Section 5):

- Screening for study eligibility and informed consent
- 4D CTA imaging at baseline and at 1-year intervals over a period of 5 years. (Annual CTA studies will be performed routinely in some or many of the patients, but the 4D protocol will be for research purposes.)
- Annual office visits and echocardiography studies over the 5-year study period (standard of care)

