3.2 Study Measures

Image-derived measures of BAV morphology and dynamics

Features of BAV morphology and motion will be extracted from 4D CTA images acquired at baseline and at 1-year intervals over a period of 5 years. Manual and automated segmentation and deformable modeling algorithms similar to those presented in (Pouch et al., 2012) and (Pouch et al., 2015) will be used generate a 4D model of the BAV apparatus in each 4D CTA scan, which will depict BAV morphology and dynamics over one complete cardiac cycle. The measures extracted from each model will include, but are not limited, to the following:

- Cusp surface areas over the cardiac cycle
- Cusp height (geometric and effective)
- Cusp free margin length
- Cusp thickness (including raphe thickness, if applicable)
- Commissural height
- Characteristics of cusp fusion (e.g., symmetric cusp geometry or cusp fusion angle for asymmetric valves)
- Aortic root dimensions (e.g., sinotubular junction diameter/area, sinus of Valsalva diameter/area, aortic annular geometry, ventriculoaortic junction diameter/area, root volume)
- Coaptation height at diastole
- Cusp displacement over the cardiac cycle
- Cusp velocity/acceleration over the cardiac cycle
- Geometry of the ascending aorta (e.g., aortic size)

Measures from office visits, imaging studies, and interventions

Relevant measurements will be recorded from annual office visits, other routine cardiac imaging studies (e.g., echocardiography or MRI), and interventions such as cardiac surgeries performed during the study period. These will include, but are not limited, to the following (all are collected as standard of care):

- Physical exam measurements and vital signs (e.g., height, weight, pulse)
- Severity of AI or AS (assessed on routine echocardiography)
- Measurements from other routine images (e.g., echocardiography or MRI) complementary to the 4D CTA measures listed above
- Physical intraoperative measurements, such as cusp height (if an aortic surgery is performed during the study period)

CONFIDENTIAL

2011 to June 2018, one surgeon at our center performed aortic valve replacement on 344 patients with BAV. Many more have undergone repair or have only been followed with routine echocardiogram and CT scans as they have not yet met the indications for surgery.

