We will primarily use PennChart to identify patients scheduled in our cardiology and cardiac surgical clinics who have been diagnosed with BAV. Additionally, we will be identifying patients who receive an echocardiogram at Penn and are noted to have a BAV. After identification and screening via chart review, patients will be approached by a research coordinator, either in person (in clinic, heart and vascular testing center, or inpatient wards) or via telephone to gauge interest and, if interested, schedule them for a visit in our research clinic to sign consents. Finally, we will be identifying patients through the Penn Biobank to screen and, if they meet criteria, contact to gauge interest and schedule for a clinic visit. Privacy of individuals will be maintained by communicating only in private spaces within the hospital or by phone.

4.6 *Vulnerable Populations:*

We will not enroll patients who are unable to provide consent themselves. Pregnant women and children are excluded from this study. Monetary compensation will not be provided for participation.

Although not directly targeted, mentally disabled persons, economically or educationally disadvantaged persons, and/or employees or students of the University of Pennsylvania will not be denied enrollment and any special protections and/or additional safeguards will be undertaken in order to protect the rights and welfare of these subjects from coercion or undue influence as appropriate.

5 Study Procedures

The procedures summarized in Section 3 are listed in Table 1.

Table 1: Schedule of Study Procedures

Study Phase	Screening	Observation Study Visits				
		1 (Baseline)	2	3	4	5
Visit Number						
Years from Baseline Study		0	1	2	3	4
Review Inclusion/Exclusion Criteria	X	X	X	X	X	X
Medical Record Review (routine office visits, imaging and laboratory studies, cardiac procedures)	X	X	X	X	X	X
Informed Consent	X					
4D CTA		X	X	X	X	X
Pregnancy Test		X	X	X	X	X
Adverse Event / Unanticipated Problems Assessment		X	X	X	X	X

CONFIDENTIAL

This material is the property of the University of Pennsylvania.

Does your study use MRI? (CAMRIS is the appropriate contact for all studies involving MRIs)

Yes No (If No, no CAMRIS review needed)

Does your study include pregnant women?

Yes No

Does your study involve the exposure to radiation, radiotracers and/or radiological imaging modalities?

Yes No (If No, no RRSC review is needed)

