5.1 Screening

The screening visit for eligibility assessment will include:

- Medical record review to verify documentation of a BAV, previous aortic interventions, presence of renal failure, contraindications to contrast agents, and pregnancy status. (Note: a pregnancy test will be performed prior to each 4D CTA study.) Pregnant women will be excluded from the study if they confirm pregnancy at the time of screening or if the pregnancy test prior to baseline imaging is positive.
- Informed consent

CONFIDENTIAL

5.2 *Study Intervention or Observational Phase (Give this section a name that is relevant to the design of your study)*

5.2.1

Baseline Imaging

After being identified, screened, and have provided informed consent, all patients will undergo a baseline 4D CTA imaging study. A pregnancy test will be performed in women prior to the 4D CTA study. Each 4D CTA scan will be performed according to established TAVR imaging protocols with modifications to limit radiation dose to approximately 5 mSv.

Additional baseline information may be collected (standard of care):

- Other routine imaging studies (e.g., echocardiography or MRI)
- Physical exam
- Vital signs
- Laboratory tests, including creatinine level
- Quality of life assessments

5.2.2 *Annual follow-up imaging and visits*

After baseline imaging, patients will have annual routine clinic follow up visits (1 year \pm 90 days) that will consist of the following:

- Medical history and physical (standard of care)
- Transthoracic echocardiogram (standard of care)
- Laboratory studies, including creatinine level (standard of care)
- 4D CTA (research). As annual CT scans are often standard of care in these patients, the research component will be the additional 4D imaging protocol, performed according to established TAVR imaging protocols with modifications to limit radiation dose to approximately 5 mSv.

5.3 *Unscheduled Visits and Surgeries*

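### The protocol states two renal exclusions for research contrast, eGFR < 30 and creatinine > 2 mg/dL, and they do not select the same patients

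*Protocol*

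**What the plan says.** Three places in the available protocol text bear on renal eligibility.

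- Study Summary, main exclusion criteria: "Renal failure (estimated Glomerular Filtration Rate (eGFR) < 30), precluding them from receiving intravenous contrast". No unit and no estimating equation are given.
- Section 1, Introduction: "Patients who are pregnant, have renal insufficiency (creatinine > 2 mg/dL), or who have a contraindication to intravenous contrast will be excluded".
- Section 5.1, Screening: the medical record is reviewed for, among other things, "presence of renal failure, contraindications to contrast agents, and pregnancy status". This repeats the Summary's term but sets no limit.

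Table 1 in Section 5 has a row, "Review Inclusion/Exclusion Criteria", marked at screening and at each of the five visits. Creatinine is among the standard-of-care laboratory values that may be collected at baseline (Section 5.2.1) and among those listed for the annual follow-up (Section 5.2.2).

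On the imaging schedule, Section 3.1 gives "4D CTA imaging at baseline and at 1-year intervals over a period of 5 years" and Section 3.2 describes images "acquired at baseline and at 1-year intervals over a period of 5 years". Table 1 marks a 4D CTA at visits 1 to 5, which fall at years 0, 1, 2, 3 and 4.

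**The concern.** Both statements are written as exclusions for the same study and serve the same purpose, deciding who may receive intravenous contrast. They differ in label (failure against insufficiency), in measure (eGFR against serum creatinine) and in cut-off. If the two rules picked out the same patients, this would be a matter of style. If they do not, the same patient can be properly enrolled according to one page and an eligibility deviation according to another.

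What is at stake is safety and conduct more than inference. Section 7 names radiation and contrast as the sources of potential safety issues, and Section 10.1 expects some participants to be scanned for research alone. The comparison of competent and incompetent valves and the sample-size reasoning in Section 6.1 do not depend on which rule is used.

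**Working it through.** **1. Are the rules equivalent?** One rule is a fixed creatinine. The other is a fixed eGFR, and eGFR at a given creatinine changes with age and sex. The study enrols men and women from 18 years, with no upper age limit in the available text. One creatinine cut-off therefore cannot match one eGFR cut-off across the study population. This needs no particular equation; only the size of the gap does.

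**2. Assumed equations.** The protocol names none, so two are taken as assumptions (Scr in mg/dL, age in years):

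- CKD-EPI 2021, for Scr above κ: eGFR = 142 × (Scr/κ)^(−1.2) × 0.9938^age × s, with κ = 0.9 and s = 1 in men, κ = 0.7 and s = 1.012 in women.
- MDRD: eGFR = 175 × Scr^(−1.154) × age^(−0.203) × s, with s = 1 in men and 0.742 in women; no race term.

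Example, man aged 20, Scr 2.0:

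- CKD-EPI 2021: 142 × (2/0.9)^(−1.2) × 0.9938^20 = 48.1
- MDRD: 175 × 2^(−1.154) × 20^(−0.203) = 42.8

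**3. eGFR at creatinine 2.0 mg/dL.** Ages 20 to 50 follow Section 1.1: "BAV patients who present with AI typically range in age from 20 to 50 years old".

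| | Age 20 | Age 35 | Age 50 |
|---|---|---|---|
| Men, CKD-EPI 2021 | 48.1 | 43.8 | 39.9 |
| Men, MDRD | 42.8 | 38.2 | 35.5 |
| Women, CKD-EPI 2021 | 36.0 | 32.8 | 29.9 |
| Women, MDRD | 31.8 | 28.4 | 26.4 |

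The combined range is 35.5 to 48.1 in men, all above 30, and 26.4 to 36.0 in women, on both sides of 30. In women the value falls below 30 from about age 27 under MDRD and about age 49 under CKD-EPI 2021.

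**4. The reverse: creatinine at which eGFR equals 30.** Solving each equation for Scr:

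- CKD-EPI 2021: Scr = κ × (142 × 0.9938^age × s / 30)^(1/1.2)
- MDRD: Scr = (175 × age^(−0.203) × s / 30)^(1/1.154)

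| | Age 20 | Age 35 | Age 50 |
|---|---|---|---|
| Men, CKD-EPI 2021 | 2.96 | 2.74 | 2.54 |
| Men, MDRD | 2.72 | 2.47 | 2.32 |
| Women, CKD-EPI 2021 | 2.33 | 2.15 | 1.99 |
| Women, MDRD | 2.10 | 1.90 | 1.79 |

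**5. A patient on each side.**

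- A man aged 30 with creatinine 2.2 mg/dL is excluded by the Introduction. His eGFR reaches 30 only at 2.53 (MDRD) or 2.81 (CKD-EPI 2021), so the Summary does not exclude him.
- A woman aged 70 with creatinine 1.9 mg/dL is not excluded by the Introduction. Her eGFR reaches 30 at 1.69 (MDRD) or 1.80 (CKD-EPI 2021), so the Summary excludes her.

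The disagreement runs both ways under both equations, so neither rule can be read as simply the stricter form of the other.

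**6. Scan wording.** Baseline plus yearly intervals over five years can be counted as years 0 to 5 (six scans) or as five annual scans at years 0 to 4. Table 1 has the latter, and Section 5 presents Table 1 as the listing of the Section 3 procedures.

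**The case against.** **The operative rule may lie elsewhere.** The Summary gives only the main criteria and the Introduction is narrative. The available text moves from Section 3.2 to the end of the recruitment text before Section 4.6, so a full eligibility list in Section 4 may settle the matter. Section 5.1 also uses the Summary's term. This stands as a limit: it cannot be said that staff lack a single working rule. But the Summary and the Introduction disagree whatever Section 4 holds, so at least one of them would need correcting. The two rules might also be applied together, excluding anyone who meets either, but the protocol does not say so.

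**The figures come from outside.** True, and they are assumptions. CKD-EPI 2021 is by its name later than the protocol's last dated amendment (June 2020). The age range describes patients presenting with AI, while about half of the study is to have no or mild AI. Widening to ages 18 to 80 gives 32 to 49 in men and 24 to 37 in women at creatinine 2.0 mg/dL. The conclusion is unchanged, and it does not rest on these values.

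**Stronger readings that a reader might infer.**

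- That the renal conflict governs every contrast scan. Table 1 does list a criteria review at each visit, but no available passage says what follows if a renal limit is crossed after enrolment, and Section 5.4 does not mention renal function.
- That the text orders six scans against five in Table 1, with a dose ceiling of 30 against 25 mSv. No passage says six scans or a year-5 scan, the wording has a reading that agrees with Table 1, and Sections 10.1 and 10.3 make 5 mSv per scan a target, not a cap. This is an ambiguity, not a contradiction.

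**Conclusion.** The renal mismatch holds. The Study Summary and the Introduction give different, non-equivalent exclusions, Section 5.1 supplies no threshold, and nothing in the available text reconciles them. It should be corrected because it decides who receives research contrast.

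Under the two assumed equations and ages 20 to 50, creatinine 2.0 mg/dL corresponds to an eGFR of about 36 to 48 in men and 26 to 36 in women. In men the creatinine rule excludes more patients under both equations; in women the direction depends on age and equation. The number of patients between the rules is unknown and may be few. The group comparison and the sample-size rationale are not affected.

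The finding covers only the sections available, not the missing part of Section 4. It does not extend to how renal function is handled after enrolment, and it does not say which limit is right. The scan schedule is a wording note only.

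**What to change.** Reconcile the passages. State one renal exclusion, chosen by the investigators, in identical terms in the Study Summary, the Introduction, the Section 4 eligibility list and Section 5.1. If it is expressed as eGFR, give the unit and the estimating equation. Check the consent text against it.

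In the same amendment, the wording of Sections 3.1 and 3.2 could be aligned with the scan years in Table 1, once the investigators confirm that Table 1 is what they intend.

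The cost is a clarifying amendment and a consent check, with no extra patients and no change to the analysis.
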